11.3.3. Other Analyses

Exploratory endpoint variables will be analysed according to their scale using general methods as described above.

PK, PD, and biomarker exploratory analyses will be described in the SAP finalised before database lock. The population PK analysis and PD analyses will be presented separately from the main CSR.

11.3.4. Follow-Up Period Analyses

Variables will be analysed according to their scale using general methods as described above. Results will be presented overall and by initial treatment assignment. In addition, subgroup analyses will be performed for HRpQCT, DXA, vertebral radiograph, CTX-1, and P1NP based on the administration of zoledronic acid during the follow-up period (none; at Month 12; at Month 18). Also, the frequency of administration of zoledronic acid during the follow-up period will be related both to the site and to the 12 months outcome for both primary efficacy endpoints.

Appendix 1: Abbreviations and Trademarks

ADA	Anti-Drug Antibody
AE	Adverse Event
AESI	Adverse Event of Special Interest
ALT	Alanine Aminotransferase
ANCOVA	Analysis of Covariance
AST	Aspartate Aminotransferase
BMD	Bone Mineral Density
BMI	Body Mass Index
BSAP	Bone-Specific Alkaline Phosphatase
BV/TV	Bone Volume Fraction
CFR	Code of Federal Regulations
CI	Confidence Interval
CONSORT	Consolidated Standards of Reporting Trials
CRA	Clinical Research Assistant
CRO	Clinical Research Organisation
C5M	Neo-Epitope of MMP-2,9 mediated degradation of Type V Collagen
CSR	Clinical Study Report
CT	Computed Tomography
CTX-1	Carboxy-terminal Telo-peptide
DMC	Data Monitoring Committee
DXA	Dual-energy X-ray Absorptiometry
EC ₅₀	Half Maximal Efficacy Concentration
ED ₅₀	Median Effective Dose
ECG	Electrocardiogram
eCRF	Electronic Case Report Form
eGFR	Estimated Glomerular Filtration Rate
EMA	European Medicines Agency
EOT	End of Treatment
EQ-5D-5L	EuroQol 5-dimension 5-level descriptive system
EUDRACT	European Union Drug Regulatory Agency Clinical Trial
FAS	Full Analysis Set
FDA	Food and Drug Administration
FEA	Finite Element Analysis
FSH	Follicle Stimulating Hormone
GCP	Good Clinical Practice

HRpQCT	High Resolution Peripheral Quantitative Computed Tomography
HRT	Hormonal Replacement Therapy
IB	Investigator's Brochure
ICF	Informed Consent Form
ICH	International Conference on Harmonisation
IEC	Independent Ethics Committee
IND	Investigational New Drug
INR	International Normalised Ratio
IRB	Institutional Review Board
IWRS	Interactive Web Response System
IV	Intravenous
LSMeans	Least Square Means
mAb	Mono-clonal Antibody
MCP-Mod	Multiple Comparison Procedure Modelling
MedDRA	Medical Dictionary for Regulatory Activities
Met/Inn	Peripheral to Medullary Trabecular Bone Density Ratio
mFAS	Modified Full Analysis Set
MMP	Matrix Metalloproteinase
NOAEL	No Observed Adverse Effect Level
NTX-1	Amino-terminal Telo-peptide
OC	Osteocalcin
OI	Osteogenesis Imperfecta
OIQoL-A	Osteogenesis Imperfecta specific Quality of Life Questionnaire for Adults
P1CP	Carboxy-terminal Propeptide of Type 1 Procollagen
P1NP	Amino-terminal Propeptide of Type 1 Procollagen
PCR	Protein: Creatinine Ratio
PD	Pharmacodynamics
PK	Pharmacokinetics
PP	Per-Protocol
PRO	Patient-Reported Outcome
Pro-C5	C-terminal Pro-Peptide of Type V collagen
PTH	Parathyroid Hormone
QCT	Quantitative Computed Tomography
QoL	Quality of Life
QT _c	Corrected QT Interval
QT _{cF}	QT _c by Fridericia's correction Formula

RANKL	Receptor Activator of Nuclear Factor Kappa-B Ligand
SAE	Serious Adverse Event
SAP	Statistical Analysis Plan
SD	Standard Deviation
SF-12	Short Form 12 Health Survey
SoA	Schedule of Activities
SOP	Standard Operating Procedure
SOST	Gene Coding for Sclerostin
SUSAR	Suspected Unexpected Serious Adverse Reaction
TbN	Trabecular Number
TbTh	Trabecular Thickness
TBS	Trabecular Bone Score
TEAE	Treatment-Emergent Adverse Event
TESAE	Treatment-Emergent Serious Adverse Event
TGF- β	Transforming Growth Factor Beta
Tr. vBMD	Trabecular Volumetric Bone Mineral Density
TSH	Thyroid Stimulating Hormone
ULN	Upper Limit of Normal
VAS	Visual Analogue Scale
vBMD	Volumetric Bone Mineral Density
WOCBP	Women of Childbearing Potential

Appendix 2: Clinical Laboratory Tests

- The tests detailed in the table below will be performed by a central laboratory unless otherwise stated.
- Protocol-specific requirements for inclusion or exclusion of participants are detailed in [Section 7](#) of the protocol.
- Additional tests may be performed at any time during the study as determined necessary by the investigator or required by local regulations.

Protocol-Required Safety Laboratory Assessments

Laboratory Assessments	Parameters			
Haematology	Platelet Count	White Blood Cell count with Differential:		
	Red Blood Cell Count	Neutrophils		
	Haemoglobin	Lymphocytes		
	Haematocrit	Monocytes Eosinophils Basophils		
Clinical Chemistry ¹	Blood Urea Nitrogen	Potassium Chloride, Bicarbonate/Carbon dioxide	AST ALT Alkaline phosphatase	Total and direct bilirubin
	Creatinine	Sodium	Thyroid stimulating hormone	Total Protein
	Glucose (non-fasting)	Calcium Vitamin D	Lipase	Prothrombin Time/ international normalised ratio
Routine Urinalysis	
 • Specific gravity • pH, glucose, protein, blood, ketones by dipstick • Microscopic examination (if blood or protein is abnormal) • Albumin creatinine ratio and protein creatinine ratio to be tested at site (if albumin or protein is abnormal) 			
Other screening Tests	
 • Follicle-stimulating hormone and estradiol (as needed in women of non-childbearing potential only) • Serum or urine human chorionic gonadotropin pregnancy test (as needed for women of childbearing potential)² 			

	
 The estimated glomerular filtration rate (eGFR) will be calculated based on Cockcroft-Gault formula: $\text{eGFR} = ((140 - \text{Age}) / (\text{SerumCreat})) * (\text{Weight}/72)$ All study-required laboratory assessments will be performed by a central laboratory, with the exception of COL1A1/COL1A2 genotyping. The results of each test must be entered into the eCRF.

NOTES:
 
¹ Details of liver chemistry stopping criteria and required actions and follow-up assessments after liver stopping or monitoring event are given in Section 9.1. All events of ALT $\geq 3 \times$ ULN and bilirubin $\geq 2 \times$ ULN (>35% direct bilirubin) or ALT $\geq 3 \times$ ULN and international normalised ratio (INR) >1.5, if INR measured which may indicate severe liver injury (possible Hy's Law), must be reported as an SAE (excluding studies of hepatic impairment or cirrhosis).
 
² Local urine testing will be standard for the protocol unless serum testing is required by local regulation or IRB/IEC.
	

Investigators must document their review of each laboratory safety report.

Laboratory/analyte results that could unblind the study will not be reported to investigative sites or other blinded personnel until the study has been unblinded.

Appendix 3: Study Governance Considerations

Regulatory and Ethical Considerations

- This study will be conducted by Mereo and ICON in accordance with the protocol and with:
 - Consensus ethical principles derived from international guidelines including the Declaration of Helsinki and Council for International Organisations of Medical Sciences International Ethical Guidelines
 - Applicable International Conference on Harmonisation (ICH) Good Clinical Practice (GCP) Guidelines
 - Applicable laws and regulations
- The protocol, protocol amendments, ICF, IB, and other relevant documents (eg, advertisements) must be submitted to an IRB/IEC by the investigator and reviewed and approved by the IRB/IEC before the study is initiated.
- Any amendments to the protocol will require IEC/IRB approval before implementation of changes made to the study design, except for changes necessary to eliminate an immediate hazard to study participants.
- In case of substantial amendment approval from the Competent Authority (or relevant regulatory agencies) will be sought by Mereo prior to implementation.
- The investigator will be responsible for the following:
 - Providing written summaries of the status of the study to the IRB/IEC annually or more frequently in accordance with the requirements, policies, and procedures established by the IRB/IEC
 - Notifying the IRB/IEC of SAE or other significant safety findings as required by IRB/IEC procedures
 - Overall conduct of the study at the site and adherence to requirements of 21 Code of Federal Regulations (CFR), ICH guidelines, the IRB/IEC, European regulation 536/2014 for clinical studies (if applicable), and all other applicable local regulations

Financial Disclosure

Investigators and sub-investigators will provide the sponsor with sufficient, accurate financial information in accordance with local regulations to allow the sponsor to submit complete and accurate financial certification or disclosure statements to the appropriate regulatory authorities. Investigators are responsible for providing information on financial interests during the course of the study and for 1 year after completion of the study.

Informed Consent Process

- The investigator or his/her representative will explain the nature of the study to the participant or his/her legally authorised representative and answer all questions regarding the study.
- Participants must be informed that their participation is voluntary. Participants or their legally authorised representative will be required to sign a statement of informed consent that meets the requirements of 21 CFR 50, local regulations, ICH guidelines, Health

Insurance Portability and Accountability Act (HIPAA) requirements, where applicable, and the IRB/IEC or study centre.

- The medical record must include a statement that written informed consent was obtained before the participant was enrolled in the study and the date the written consent was obtained. The authorised person obtaining the informed consent must also sign the ICF.
- Participants must be re-consented to the most current version of the ICF(s) during their participation in the study.
- A copy of the ICF(s) must be provided to the participant or the participant's legally authorised representative.

Data Protection

- Participants will be assigned a unique identifier by the sponsor. Any participant records or datasets that are transferred to the sponsor will contain the identifier only; participant names or any information which would make the participant identifiable will not be transferred.
- The participant must be informed that his/her personal study-related data will be used by the sponsor in accordance with local data protection law. The level of disclosure must also be explained to the participant.
- The participant must be informed that his/her medical records may be examined by Clinical Quality Assurance auditors or other authorised personnel appointed by the sponsor, by appropriate IRB/IEC members, and by inspectors from regulatory authorities.

Committees Structure

A Data Monitoring Committee (DMC) will be established to review the efficacy and safety results. The DMC will have access to unblinded data. Based on the data the DMC will submit its recommendations in written form to the sponsor who is responsible for responding to the recommendations of the DMC and to take appropriate action. The investigators will only be informed by the sponsor in case of stopping the trial. The DMC may choose to request additional evaluations at any time if they feel this is warranted from the standpoint of safety.

The DMC will act according to its own written standard operating procedure (SOP) described in a charter and will prepare written minutes of its meetings.

Publication Policy

The sponsor shall retain the ownership of all data. When the study is complete the sponsor shall arrange the analysis and tabulation of data. A CSR shall then be prepared, which may be used for publication, presentation at scientific meetings or submission to regulatory authorities. All proposed publications based on this study must be participant to the sponsor's approval requirements.

The sponsor will comply with the requirements for publication of study results. In accordance with standard editorial and ethical practice, the sponsor will generally support publication of

multicentre studies only in their entirety and not as individual site data. In this case, a coordinating investigator will be designated by mutual agreement.

Authorship will be determined by mutual agreement and in line with International Committee of Medical Journal Editors authorship requirements.

Dissemination of Clinical Study Data

At the end of the study, investigators will be informed of the outcome of the study including the treatment allocation as soon as the results are available and can be reported. These may be shared with participants in the study.

The sponsor assures that the key design elements of this protocol will be posted in a publicly accessible database such as clinicaltrials.gov. In addition, upon study completion and finalisation of the study report, the results of this trial will be submitted for publication and/or posted in a publicly accessible database of clinical trial results.

Data Quality Assurance

- All participant data relating to the study will be recorded on printed or eCRF unless transmitted to the sponsor or designee electronically (eg, laboratory data). The investigator is responsible for verifying that data entries are accurate and correct by physically or electronically signing the eCRF.
- The investigator must maintain accurate documentation (source data) that supports the information entered in the eCRF.
- The investigator must permit study-related monitoring, audits, IRB/IEC review, and regulatory agency inspections and provide direct access to source data documents.
- The sponsor or designee is responsible for the data management of this study including quality checking of the data.
- Study monitors will perform ongoing source data verification to confirm that data entered into the eCRF by authorised site personnel are accurate, complete, and verifiable from source documents; that the safety and rights of participants are being protected; and that the study is being conducted in accordance with the currently approved protocol and any other study agreements, ICH GCP, and all applicable regulatory requirements.
- Records and documents, including signed ICF, pertaining to the conduct of this study must be retained by the investigator for 2 years after the last approval of a marketing application in an ICH region unless local regulations or institutional policies require a longer retention period. No records may be destroyed during the retention period without the written approval of the sponsor. No records may be transferred to another location or party without written notification to the sponsor.

Source Documents

- Source documents provide evidence for the existence of the participant and substantiate the integrity of the data collected. Source documents are filed at the investigator's site.
- Data reported on the eCRF or entered in the eCRF that are transcribed from source documents must be consistent with the source documents or the discrepancies must be explained. The investigator may need to request previous medical records or transfer records, depending on the study. Also, current medical records must be available.
- Definition of what constitutes source data can be found in the Study Manual and Monitoring Plan.

Study and Site Closure

The sponsor or its designee may stop the study or study site participation in the study for medical, safety, regulatory, administrative, or other reasons consistent with applicable laws, regulations, and GCP.

Appendix 4: Adverse Events: Definitions and Procedures for Recording, Evaluating, Follow-up, and Reporting

Definition of AE

AE Definition

 • An AE is any untoward medical occurrence in a patient or clinical trial subject administered a medicinal product and which does not necessarily have a causal relationship with this treatment. • NOTE: An AE can therefore be any unfavorable and unintended sign (e.g. an abnormal laboratory finding), symptom, or disease (new or exacerbated) whether or not considered related to the medicinal product.

Events Meeting the AE Definition

 • Any abnormal laboratory test results (haematology, clinical chemistry, or urinalysis) or other safety assessments (eg, ECG, radiological scans, vital signs measurements), including those that worsen from baseline, considered clinically significant in the medical and scientific judgment of the investigator (ie, not related to progression of underlying disease). • Exacerbation of a chronic or intermittent pre-existing condition including either an increase in frequency and/or intensity of the condition. • New conditions detected or diagnosed after study treatment administration even though it may have been present before the start of the study. • Signs, symptoms, or the clinical sequelae of a suspected drug-drug interaction. • Signs, symptoms, or the clinical sequelae of a suspected overdose of either study treatment or a concomitant medication. Overdose per se will not be reported as an AE/SAE unless it is an intentional overdose taken with possible suicidal/self-harming intent. Such overdoses should be reported regardless of sequelae. • "Lack of efficacy" or "failure of expected pharmacological action" per se will not be reported as an AE or SAE. Such instances will be captured in the efficacy assessments. However, the signs, symptoms, and/or clinical sequelae resulting from lack of efficacy will be reported as AE or SAE if they fulfill the definition of an AE or SAE.

Events NOT Meeting the AE Definition

- Any clinically significant abnormal laboratory findings or other abnormal safety assessments which are associated with the underlying disease, unless judged by the investigator to be more severe than expected for the participant's condition.
- The disease/disorder being studied or expected progression, signs, or symptoms of the disease/disorder being studied, unless more severe than expected for the participant's condition.
- Medical or surgical procedure (eg, endoscopy, appendectomy): the condition that leads to the procedure is the AE.
- Situations in which an untoward medical occurrence did not occur (social and/or convenience admission to a hospital).
- Anticipated day-to-day fluctuations of pre-existing disease(s) or condition(s) present or detected at the start of the study that do not worsen.

Definition of SAE

If an event is not an AE per definition above, then it cannot be an SAE even if serious conditions are met (eg, hospitalisation for signs/symptoms of the disease under study, death due to progression of disease).

A SAE is defined as any untoward medical occurrence that, at any dose:

a. Results in death

b. Is life-threatening

The term 'life-threatening' in the definition of 'serious' refers to an event in which the participant was at risk of death at the time of the event. It does not refer to an event, which hypothetically might have caused death, if it were more severe.

c. Requires inpatient hospitalisation or prolongation of existing hospitalisation

In general, hospitalisation signifies that the participant has been detained (usually involving at least an overnight stay) at the hospital or emergency ward for observation and/or treatment that would not have been appropriate in the physician's office or outpatient setting. Complications that occur during hospitalisation are AE. If a complication prolongs hospitalisation or fulfills any other serious criteria, the event is serious. When in doubt as to whether "hospitalisation" occurred or was necessary, the AE should be considered serious.

Hospitalisation for elective treatment of a pre-existing condition that did not worsen from baseline is not considered an AE.

d. Results in persistent disability/incapacity
 
 • The term disability means a substantial disruption of a person's ability to conduct normal life functions. • This definition is not intended to include experiences of relatively minor medical significance such as uncomplicated headache, nausea, vomiting, diarrhea, influenza, and accidental trauma (eg, sprained ankle) which may interfere with or prevent everyday life functions but do not constitute a substantial disruption.

e. Is a congenital anomaly/birth defect


f. Other situations:
 
 • Medical or scientific judgment should be exercised in deciding whether SAE reporting is appropriate in other situations such as important medical events that may not be immediately life-threatening or result in death or hospitalisation but may jeopardise the participant or may require medical or surgical intervention to prevent one of the other outcomes listed in the above definition. These events should usually be considered serious. 
Examples of such events include invasive or malignant cancers, intensive treatment in an emergency room or at home for allergic bronchospasm, blood dyscrasias or convulsions that do not result in hospitalisation, or development of drug dependency or drug abuse.

Definition of AESI

An adverse event of special interest (serious or non-serious) is one of scientific and medical concern specific to the sponsor's product or program, for which ongoing monitoring and rapid communication by the investigator to the sponsor can be appropriate. Such an event might warrant further investigation in order to characterise and understand it. Depending on the nature of the event, rapid communication by the trial sponsor to other parties (e.g. regulators) might also be warranted (CIOMS VI and ICH E2F)

AESIs for setrusumab

Some AEs, despite their severity or outcome, will be expedited due to the relevance for participant safety or study treatment safety profile. These events should be reported to the Sponsor/designee within 24 hours. This is to enable follow-up to be performed on all these reported adverse events that have not been reported as serious adverse events (SAEs). The AESIs for setrusumab are:
 
 • Fractures • Cardiovascular events 
Cardiovascular events that are considered to be clinically significant by the PI and/ or medical team will also be submitted to the independent DMC for CV adjudication.

Recording AE and SAE/AESI

AE and SAE/AESI Recording

- When an AE/SAE/AESI occurs, it is the responsibility of the investigator to review all documentation (eg, hospital progress notes, laboratory, and diagnostics reports) related to the event.
- The investigator will then record all relevant AE/SAE/AESI information in the SAE/AESI report form and the eCRF.
- It is **not** acceptable for the investigator to send photocopies of the participant's medical records to the Safety CRO in lieu of completion of the SAE/AESI report form.
- There may be instances when copies of medical records for certain cases are requested by the Safety CRO. In this case, all participant identifiers, with the exception of the participant number, will be blinded on the copies of the medical records before submission to the Safety CRO.
- The investigator will attempt to establish a diagnosis of the event based on signs, symptoms, and/or other clinical information. In such cases, the diagnosis (not the individual signs/symptoms) will be documented as the AE/SAE/AESI.

Assessment of Intensity

The investigator will make an assessment of intensity for each AE and SAE/AESI reported during the study and assign it to one of the following categories:

- **Mild:** An event that is easily tolerated by the participant, causing minimal discomfort and not interfering with everyday activities.
- **Moderate:** An event that causes sufficiently discomfort and interferes with normal everyday activities.
- **Severe:** An event that prevents normal everyday activities. An AE that is assessed as severe should not be confused with an SAE. Severe is a category utilised for rating the intensity of an event; and both AE and SAE can be assessed as severe.

An event is defined as 'serious' when it meets at least 1 of the predefined outcomes as described in the definition of an SAE, NOT when it is rated as severe.

Assessment of Causality

- The investigator is obligated to assess the relationship between study treatment and each occurrence of each AE/SAE/AESI.
- A "reasonable possibility" of a relationship conveys that there are facts, evidence, and/or arguments to suggest a causal relationship, rather than a relationship cannot be ruled out.
- The investigator will use clinical judgment to determine the relationship.
- Alternative causes, such as underlying disease(s), concomitant therapy, and other risk factors, as well as the temporal relationship of the event to study treatment administration will be considered and investigated.
- The investigator will also consult the IB and/or Product Information, for marketed products, in his/her assessment.

- For each AE/SAE/AESI, the investigator **must** document in the medical notes that he/she has reviewed the AE/SAE/AESI and has provided an assessment of causality.
- There may be situations in which an SAE/AESI has occurred and the investigator has minimal information to include in the initial report to the Safety CRO. However, **it is very important that the investigator always make an assessment of causality for every event before the initial transmission of the SAE/AESI data to the Safety CRO.**
- The investigator may change his/her opinion of causality in light of follow-up information and send an SAE/AESI follow-up report with the updated causality assessment.
- The causality assessment is one of the criteria used when determining regulatory reporting requirements.

Follow-up of AE and SAE/AESI

- The investigator is obligated to perform or arrange for the conduct of supplemental measurements and/or evaluations as medically indicated or as requested by the Safety CRO to elucidate the nature and/or causality of the AE or SAE/AESI as fully as possible. This may include additional laboratory tests or investigations, histopathological examinations, or consultation with other health care professionals.
- If a participant dies during participation in the study or during a recognised follow-up period, the investigator will provide the Safety CRO with a copy of any post-mortem findings including histopathology.
- New or updated information will be recorded in the SAE/AESI report form and completed eCRF.
- The investigator will submit any updated SAE/AESI data to the sponsor within 24 hours of receipt of the information.

SAE Reporting to the Safety CRO via SAE/AESI Report Form

- The primary mechanism for reporting SAE/AESI to the Safety CRO will be the SAE/AESI report form.
- The site will submit the SAE/AESI data on the SAE/AESI report form as soon as it becomes available.
- Facsimile transmission of the SAE/AESI report form is the preferred method to transmit this information to the Safety CRO Drug Safety team. The following contacts may be used:

[contact]

In case of issues with fax, Email: [contact]

- Contacts for SAE/AESI reporting can be found in above or in the MBPS205 Investigator Site File.

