4.1. Background

Osteogenesis imperfecta (OI) is a serious and debilitating genetic disorder that is characterised by fragile bones that break easily, often with little or no physical trauma. Patients may suffer from recurrent fractures, bone deformity, bone pain, muscle weakness, hearing loss, fatigue, joint laxity, curved bones, scoliosis and short stature. In the most severe cases, OI can be life-threatening. It has been shown that patients with OI have a higher mortality rate, at all ages, with an increased risk of death from respiratory diseases, gastrointestinal diseases and trauma. Basilar invagination may lead to neurological consequences. Diagnosis of OI is based on the clinical features of the disease but may be confirmed by collagen or DNA testing. OI comprises of a group of disorders which primarily arise from mutation in the genes encoding Type I collagen. In about 85% of cases, autosomal dominant OI is caused by mutations in COL1A1 and COL1A2 genes (17q21.33 and 7q21.3) which encode the alpha 1 and 2 chains of Type 1 collagen. Autosomal recessive forms of OI are also observed and are caused by mutations in the LEPRE1, CRTAP, and PPIB genes (1p34.1, 3p22 and 15q21-q22). Autosomal recessive forms are in most cases severe or even lethal ([Willaert et al, 2009](#); [Ward et al, 2002](#); [Lindahl et al, 2014](#); [Valadares et al, 2014](#)).

Setrusumab is a fully human anti-sclerostin neutralising monoclonal antibody. Sclerostin, encoded for by the SOST gene, is an osteocyte-secreted glycoprotein and is functionally a negative regulator of bone formation. Lack of sclerostin in humans (sclerosteosis) ([Online Mendelian Inheritance in Man \[OMIM\] entry #269500](#)) and van Buchem disease ([OMIM entry #239100](#)) results in life-long increased bone formation in the entire skeleton leading to increased bone mineral mass, density and strength ([Balemans et al 2001](#); [Brunkow et al 2001](#); [Balemans et al 2002](#); [Stahling-Hampton et al 2002](#)).

Setrusumab has an affinity of 21 pM for human sclerostin and reverses the human sclerostin-mediated inhibition of canonical Wnt signalling and in vitro bone mineralisation, a surrogate assay for bone formation, with EC₅₀ values of 13 nM and 150 nM, respectively.

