8.6.1.1 Adverse Events of Special Interest

The AESIs for setrusumab are:

- Fractures
- Cardiovascular events

The frequency and incidence of all treatment emergent AESIs will be presented by system organ class and preferred term for each treatment group.

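### Appendix 4 gives conflicting rules for fractures: the disease-under-study exclusion can make a hospitalised fracture of expected severity a non-AE and non-SAE, while the AESI list makes every fracture an adverse event

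*Protocol*

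**What the plan says.** Three parts of Protocol Appendix 4 bear on how a fracture is classified.

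- **AE exclusion.** Among the events that do not meet the AE definition is: "The disease/disorder being studied or expected progression, signs, or symptoms of the disease/disorder being studied, unless more severe than expected for the participant's condition".
- **SAE definition.** This opens with: "If an event is not an AE per definition above, then it cannot be an SAE even if serious conditions are met". The examples given are "hospitalisation for signs/symptoms of the disease under study, death due to progression of disease". Inpatient hospitalisation is nonetheless seriousness criterion (c).
- **AESI list.** An AESI is defined as a type of adverse event that may be serious or non-serious. The section says: "Some AEs, despite their severity or outcome, will be expedited due to the relevance for participant safety or study treatment safety profile". It sets a 24-hour reporting limit and names two AESIs, fractures and cardiovascular events. The fracture entry carries no condition on severity or cause.

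Protocol section 4.1 describes fracture as part of the disease: "Patients may suffer from recurrent fractures, bone deformity, bone pain, muscle weakness, hearing loss". Inclusion criterion 3 (section 7.1) requires at least one non-traumatic fracture in the past 5 years.

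On the analysis side, SAP 7.1.4.1 defines a treatment-emergent event (TEAE) as an AE that occurs or worsens after first dose. SAP 8.6.1 tabulates serious TEAEs, and SAP 8.6.1.1 says: "The frequency and incidence of all treatment emergent AESIs will be presented by system organ class and preferred term". The follow-up Schedule of Activities (Protocol section 3) limits event reporting to SAEs after Month 14.

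**The concern.** In most trials, excluding expected disease signs from the AE definition is harmless. Here the main disease sign is also a listed event of special interest, so the same fracture falls under two rules that give opposite answers. Two sites could classify identical fractures differently, and both could point to Appendix 4 in support.

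What is at stake is the meaning of the safety counts. Protocol section 6.5 selects the dose on benefit/risk, using HRpQCT results and safety. If some sites record every fracture as an AESI and others only those judged worse than expected, the AESI table mixes two quantities. The serious-TEAE table has the same problem for hospitalised fractures. After Month 14 the question becomes whether a fracture enters safety reporting at all, because only SAEs are then reported.

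**Working it through.** No power or event-rate calculation applies, so the check is to follow one case through the text. Take a participant admitted to hospital with a low-trauma long-bone fracture that is no more severe than expected for that person.

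1. **Is it an AE under the exclusion?** Fracture is an expected sign of OI (section 4.1; inclusion criterion 3). It is not more severe than expected. Result: not an AE.
2. **Is it an SAE under that reading?** It meets criterion (c), inpatient hospitalisation. As a non-AE it is barred from being an SAE, and it matches the first example given with the bar. Result: not an SAE.
3. **Is it an AE under the AESI list?** Fractures are named without qualification, AESIs are adverse events, and severity does not matter. Result: an AE and an AESI.
4. **Is it an SAE under that reading?** The AESI section wants follow-up of AESIs that were not reported as SAEs, so it expects that some will be. Criterion (c) is met. Result: an SAE, but in conflict with the example in step 2.
5. **Does anything settle the order of precedence?** Protocol sections 10.1.1.3, 10.2 and 11.3.2, both Schedules of Activities, Appendix 4, and SAP 7.1.4.1, 8.6.1 and 8.6.1.1 contain no such statement. No text exempts fractures from the exclusion.

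The two readings compared by type of fracture:

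| Fracture | Exclusion governs | AESI list governs |
|---|---|---|
| More severe than expected | AE; SAE if a criterion is met | AE/AESI; SAE if a criterion is met |
| Expected severity, no seriousness criterion met | Not an AE | AE/AESI, non-serious |
| Expected severity, hospitalised | Not an AE, not an SAE | AE/AESI and SAE |

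The first row is the same under both readings apart from the AESI label. The second row changes the AESI and TEAE tables. The third also changes the serious-TEAE table and decides whether the fracture is reported after Month 14.

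**Size.** The documents give no expected fracture rate and no share of fractures that would count as more severe than expected, so the number of affected events cannot be derived. With 25 participants per arm (Protocol section 11.1), one reclassified participant changes an arm's incidence by 1/25 = 4 percentage points.

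**The case against.** The strongest reply is that a specific rule displaces a general one. Fractures are named outright, severity is declared irrelevant, and Protocol section 10.2.1 requires every AESI to be reported within 24 hours. Many investigators would report every fracture on that basis. This has force for AESI recording, but no text says so, and it leaves seriousness open. The SAE bar refers back to the AE definition, the AESI list comes after it, and the hospitalisation example still stands.

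Several other points against the concern stand and limit it.

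- The exclusion is not absolute. Events more severe than expected remain AEs, and Appendix 4 also counts an increase in frequency or intensity of a pre-existing condition as an AE. A reader might infer that fractures can never be SAEs; the text does not go that far. The exceptions do, however, add a judgement for which no criteria are given.
- Fracture efficacy data do not pass through the AE definition. Symptomatic fractures are assessed throughout and centrally read (Protocol 10.1.1.3), and SAP 8.5.3.9 analyses them by arm. The comparison of fractures between doses survives.
- Investigators in the three blinded arms do not know the dose, so inconsistent coding would not be expected to favour one of those doses.

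Some wider inferences are tempting but unsupported.

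- **Deaths.** Section 4.1 reports higher mortality in OI from respiratory, gastrointestinal and trauma causes. It does not call such deaths disease progression, and death is seriousness criterion (a).
- **Cardiovascular events.** Nothing describes them as signs of OI, so no conflict is shown.
- **Data monitoring committee.** What it sees is set by a separate charter and analysis plan. Appendix 3 gives it unblinded efficacy and safety results and lets it request further evaluations. Loss of fracture data from its review is not shown.
- **One centre shifting an arm by several events.** About 100 participants over about 28 centres is 100/28 = 3.6 per centre, or 3.6/4 = 0.9 per arm per centre. An average centre could not do this unless a participant had repeat fractures.

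**Conclusion.** The conflict is real and is shown by the text alone. For a hospitalised fracture of expected severity, Appendix 4 gives two incompatible classifications and no order of precedence. The conflict is sharpest for seriousness and weaker, though still unresolved, for AESI recording.

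Its reach is limited to safety outputs: the TEAE, AESI and serious-TEAE tables, and SAE-only reporting after Month 14. The efficacy fracture endpoints are unaffected. The direction is clear, since the AESI rule counts more fractures than the exclusion does. The overall size is not known.

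The conclusion rests on one reading of the documents, that an ordinary fracture in this population is an expected sign of the disease. Section 4.1 and inclusion criterion 3 support that reading.

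**What to change.** State in Protocol Appendix 4 that the disease-under-study exclusion, and the hospitalisation example in the SAE definition, do not apply to events on the AESI list. Every on-study fracture is then recorded as an AE and AESI, and its seriousness is judged by criteria (a) to (f) alone. Tell sites of the clarification so that all apply one rule.

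Separate rows for serious and non-serious AESIs in SAP 8.6.1.1 would help the reader but are optional, because SAP 8.6.1 already tabulates serious TEAEs by preferred term.

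The cost is an appendix edit and a notice to sites. There will be more fracture SAE reports to process and a higher SAE count, which should be explained when the results are presented.
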